6.8. Concomitant Therapy

For All Participants

Prestudy specific therapies such as analgesics/antipyretics and non-steroidal anti-inflammatory drugs (NSAIDs) administered up to 30 days before the dose of study vaccine must be recorded at screening. Use of analgesics/antipyretics and NSAIDs for routine prophylaxis prior to study vaccine administration is discouraged, however, should be used only in case of medical need and in line with local standard of care.

Concomitant therapies associated with SAEs, AESIs, and with AEs leading to discontinuation from study will be collected and recorded in the eCRF from the time of vaccination through the end of the study. Concomitant medications associated with RSV, hMPV, and influenza-mediated ARI episodes and with complications of RSV, hMPV, and influenza-mediated ARIs will be captured in the eCRF for the duration of the study.

The use of systemic corticosteroids must be documented throughout the study. Antineoplastic and immunomodulating agents, eg, cancer chemotherapeutic agents or chronic or recurrent use of systemic corticosteroids, or radiotherapy are prohibited throughout the study. If the use of systemic corticosteroids, antineoplastic or immunomodulating agents becomes medically indicated during the study for any participant, the sponsor should be contacted.

Vaccination with licensed live-attenuated vaccines within 28 days of the study vaccination (ie, before or after) is prohibited. Other licensed (not live) vaccines (eg, tetanus, hepatitis A or B, rabies) should be given at least 14 days before (or at least 14 days after) administration of study vaccine. If a vaccine is indicated in a post-exposure setting (eg, rabies or tetanus), it must take priority over the study vaccine.

For SARS-CoV-2 vaccines either licensed or available under Emergency Use Authorization: live-attenuated vaccines should be given at least 28 days before or after study vaccination; non-live vaccines should be given at least 14 days before or after study vaccination. A viral-vectored SARS-CoV-2 vaccine is not to be given within 28 days before or after study vaccination. Any history of

SARS-COV-2 vaccination (name/manufacturer of the vaccine and date of administration, whenever possible) prior to and during the study will be collected in the eCRF.

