9.3. Populations for Analyses

Vaccination assignment will follow the as-treated principle. Note that all analyses will focus on the participants enrolled in the Global cohort. Any local cohort enrolment beyond what is included in the Global cohort will be analyzed as a separate dataset apart from the Global cohort, but they will also be included in the primary analysis and final analysis if their enrollment started prior to the database cut-off of the primary analysis or final analysis, respectively.

For purposes of analysis, the following populations are defined:

- Full Analysis Set (FAS): will include all participants with a documented vaccine administration, regardless of the occurrence of protocol deviations. The FAS is the primary safety population. The analysis of solicited and unsolicited AEs will be restricted to a subset of the FAS (ie, the Safety Subset).^a
- Per-protocol Efficacy (PPE) population includes all randomized and vaccinated participants, excluding those with major protocol deviations (MPDs) expecting to impact the efficacy outcomes. Only data of the year (first year, second year) in which the MPD impacting efficacy occurs and the data of later years are excluded. The list of MPDs to be excluded from efficacy analyses will be specified in the Statistical Analysis Plan or major protocol violation criteria document, which will be finalized before database lock and unblinding. Participants with an RT-PCR-confirmed RSV-mediated ARI with onset within 14 days after vaccination, participants who discontinue within 14 days after vaccination, and participants who received vaccination within 14 days of the database cut-off date will be excluded from the PPE

^a The specification of this subset for analysis of solicited and unsolicited AEs does not preclude the investigator from reporting an AE in any participant if the investigator considers the event to be of clinical relevance and/or related to the study vaccine.

population. This analysis set will be used for analyses over the whole study period (up to database cut-off).

For analyses focusing on the first year, the PPE population is similar but only excludes MPDs occurring during the first year.

For analyses focusing on the second year, participants with MPDs expected to impact the efficacy outcomes and occurring during the second year will be additionally excluded from the PPE set defined above, as well as participants who discontinued prior to Day 365.

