The PPE population is the primary efficacy population. Sensitivity efficacy analyses will be performed on the FAS.

- Per-protocol Immunogenicity (PPI) population: will include all randomized and vaccinated participants who are part of the Immuno Subset and for whom immunogenicity data are available. Samples taken after a participant experiences an MPD expected to impact the immunogenicity outcomes will be excluded from the PPI analysis. The list of MPDs to be excluded from the immunogenicity analysis will be specified in the Statistical Analysis Plan or major protocol violation criteria document, which will be finalized before database lock and unblinding.

In addition, for participants who experience an RT-PCR-confirmed RSV-mediated ARI, samples taken after the RSV infection will not be taken into account in the assessment of the immunogenicity.

- The PPI population is the primary immunogenicity population. For key tables, sensitivity immunogenicity analyses will be performed on the FAS, including participants who are part of the Immuno Subset for whom immunogenicity measures are available. Excluded samples may be taken into account as well in the sensitivity analysis.

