9.4.1. Efficacy Analysis

9.4.1.1. Primary Endpoint

The analysis of the primary endpoint will evaluate the first occurrence of RT-PCR-confirmed RSV-mediated LRTD (for the definition, see Section 8.2, Efficacy Assessments) with onset of at least 14 days after vaccination in the active vaccine group compared to the placebo group in the PPE population. Time at risk will also be taken into account. The null hypothesis of LL \leq 20% for RT-PCR-confirmed RSV-mediated LRTD will be tested versus the alternative hypothesis of LL $>$ 20%. Additionally, the observed VE should be $>$ 50%.

Exact Poisson regression will be fitted with the event rate, defined as the number of cases (with onset at least 14 days after vaccination) over the follow-up time (off-set) as dependent variable and the vaccination group, being at increased risk of RSV disease, and age stratum (both variables as stratified; see Section 6.3) as independent variables. Each participant will be taken into account in the model with one observation indicating whether they had a case or not, the vaccination group, the stratification factors, and the follow-up time.

The follow-up time is defined as the time between 14 days post-vaccination and occurrence of the first event. For non-cases, it is the time between 14 days post-vaccination and the database cut-off date of the analysis. However, for participants who discontinued or completed the study before that date and before having an event, follow-up time is defined as the time between 14 days post-vaccination and the date of last contact.

For participants with an MPD impacting efficacy during the second year, only the first year data are taken into account: for cases during the first year, the follow-up time is defined as the time between 14 days post-vaccination and occurrence of the first event. For non-cases, it is the time between 14 days post-vaccination and the Day 365 visit. Thus, all participants will be included in the analysis according to their follow-up time.

The study is 92successful if:

- The LL of the 95% 2-sided CI (potentially corrected as described in Section 9.4.1.3) around the VE (1-relative risk rate) calculated from the Exact Poisson regression model is above 20% and additionally a point-estimate of VE >50% is observed for Group 1

Sensitivity Analyses

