As a sensitivity analysis, the above model will be repeated based on the FAS, not taking into account the restriction on the onset (at least 14 days). Additional sensitivity analyses will include:

- An exact binomial test, which does not take into account strata or follow-up time, based on the PPE population and the FAS. The VE (1-relative risk) and the corresponding corrected 2-sided CI based on the exact binomial will be calculated as well. The same alpha as in the primary analysis will be used for calculating the CI.
- If the primary analysis is performed in 2023, an exact Poisson model similar to the primary analysis will be performed including an interaction term between the treatment group and the year variables.

The analysis of the primary endpoint will be repeated, but participants with RSV infection and a co-infection with at least one other respiratory virus (ie, confirmed using the BioFire Filmarray Respiratory panel for nasal swabs, or the BioFire Filmarray PN panel for a sputum sample, when available) will not be considered as a case for that episode, as the etiology of symptoms will be indeterminate. Additionally, the analysis of the primary endpoint will be repeated, taking into account only the RT-PCR test results from the study-specified BioFire Filmarray Respiratory panel for nasal swabs and the BioFire Filmarray PN panel for a sputum sample, when available (ie, excluding hospital test results with a locally approved RT-PCR test for participants who were

hospitalized). Details on the strategy for local site and central testing of the nasal swabs and sputum samples are provided in Section 8.2.4. Another sensitivity analysis will focus on the programmed case definition of RT-PCR confirmed RSV-mediated LRTD, not taking into account the CEC adjudication.

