For participants with an MPD impacting efficacy during the second year (during the second year follow up period), only the first year data are taken into account: for cases during the first year, the follow - up time is defined as the time between 14 days post-vaccination and occurrence of the first event . For non-cases, it is the time between 14 days post - vaccination and the day before Day 365 visit (or relative day 365, in case Day 365 not available but there are ARI surveillance questions available after the relative day 365). Thus, all participants will be included in the analysis according to their follow-up time.

Note: Occurrence is always referring to the start of the ARI as reported in the CRF (CESTDTC).

As **sensitivity analyses** the above Poisson model will be repeated similar to the primary analysis:

- based on the FAS (which also does not take into account the restriction on the onset [at least 14 days] and will count follow up from vaccination on Day 1 onwards).
- based on the PPE set but excluding coinfections with other respiratory viruses, based on the Biofire - Filmarray assay (Section 7.7) or the Cepheid GeneXpert (for swabs in China sites). This should be detected in one of the scheduled nasal or sputum samples linked to the respective ARI but should not necessarily be detected in the same sample as the one that resulted in RSV confirmation.
- based on the PPE set but excluding coinfections with other respiratory viruses or bacteria, based on the Biofire - Filmarray assay (Section 7.7) or the Cepheid GeneXpert (for swabs in China sites). This should be detected in one of the scheduled nasal or sputum samples linked to the respective ARI but should not necessarily be detected in the same sample as the one that resulted in RSV confirmation.
- based on the PPE set with age and increased risk status as collected (instead of as stratified) in case there are many discrepancies between as collected and as stratified.

- based on the PPE set but excluding RSV positive tests from local hospital assays of hospitalized participants.

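### The per-protocol efficacy rule drops the whole study year in which a major deviation occurs, losing valid LRTD cases before it; censoring at the deviation would keep them

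*Protocol*

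**What the plan says.** Protocol 9.3 states the rule for MPDs expected to affect efficacy: "Only data of the year (first year, second year) in which the MPD impacting efficacy occurs and the data of later years are excluded". SAP Table 3 repeats it. The rule governs the primary test, because "The PPE population is the primary efficacy population".

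Protocol 9.4.1.1 carries it into the primary model: "For participants with an MPD impacting efficacy during the second year, only the first year data are taken into account". For participants with such an MPD and no first-year case, follow-up ends at Day 365: "For non-cases, it is the time between 14 days post-vaccination and the Day 365 visit". SAP 6.3.3 does the same ("only the first year data are taken into account: for cases during the first year"), ending follow-up on the day before the Day 365 visit. Neither document ends efficacy follow-up at the MPD itself.

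For the second-year endpoints, SAP 6.4.1.2.1 excludes anyone with an MPD in either year, and Protocol 9.3 also excludes second-year MPDs. Protocol 9.4.1.2 names first-year MPDs only.

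The immunogenicity set, defined in the same Protocol section, works differently: "Samples taken after a participant experiences an MPD expected to impact the immunogenicity outcomes will be excluded from the PPI analysis".

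The types and frequency of MPDs are not given. The list is to be finalised before database lock and unblinding, in a separate criteria document according to SAP Table 3.

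**The concern.** A deviation cannot affect a case or person-time that came before it. Under the year rule, a participant whose MPD falls in month 11 contributes nothing, including any LRTD in months 1 to 10. A second-year LRTD disappears if an MPD follows it within that year. Membership of the primary efficacy set is therefore decided partly by events after the outcome. For immunogenicity the same section drops only data after the deviation, and the documents give no reason for treating efficacy differently.

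Two things are at stake. Valid events are discarded in a trial planned on few events, and this also touches the second-year LRTD endpoint, which Protocol 9.2.1 powers at only about 80%. In addition, the VE estimate becomes sensitive to any difference between arms in how often a case is followed by an MPD. Censoring at the MPD removes that sensitivity for earlier cases, because nothing after a first event can then remove it.

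**Working it through.** **1. The plan's own figure.** Inputs from Protocol 9.2.1 and 9.5.1: null VE 20%, assumed VE 65%, 2:1 allocation, one-sided 2.5%, Pocock-like spending, 76 events for 90% power. Conditional on the total number of cases, the vaccine share is:
- null: 2×0.80/(2×0.80+1) = 0.615
- alternative: 2×0.35/(2×0.35+1) = 0.412

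An exact group-sequential calculation with spending 0.025×ln(1+(e−1)t), the added VE >50% rule and four looks ending at 76 events gives power of 90.8% to 91.3% over three assumed sets of look timings. The stated figure reproduces.

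**2. Expected events by year.** Placebo incidence is 0.2% then 0.5%, with 10% exclusions per year. The vaccine-adjusted number at risk is 7,670 + 0.35×15,340 = 13,039.
- Year 1: 0.9×0.002×13,039 = 23.5
- Year 2: 0.81×0.005×13,039 = 52.8
- Total: 76.3

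**3. Events lost relative to censoring.** Assumption: a fraction m per year has a post-vaccination MPD at a uniform time, unrelated to cases. On average half of that year precedes the MPD and is discarded without need. Loss = 0.5×m×76.3:
- m = 1%: 0.4 events (0.5%)
- m = 3%: 1.1 events (1.5%)
- m = 5%: 1.9 events (2.5%)

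A one-year model (at risk Day 14 to 365, placebo incidence 0.5%, VE 65%, no dropout) agrees. The 10% row is a ceiling at which every planned exclusion is a post-vaccination MPD.

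| MPD rate per year | Cases, year rule | Cases, censored at MPD | Loss |
|---|---|---|---|
| 1% | 64.4 | 64.8 | about 0.5% |
| 2% | 63.8 | 64.4 | about 1% |
| 5% | 61.8 | 63.4 | about 2.5% |
| 10% | 58.6 | 61.8 | about 5% |

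VE is 65.0% under both rules in every row.

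**4. Effect on power.** Schoenfeld approximation, single look: power = Φ(√(d×2/9)×ln(0.80/0.35) − 1.96).
- d = 76: Φ(4.110×0.827 − 1.96) = 92.5%
- d = 74.1 (1.9 fewer): Φ(4.058×0.827 − 1.96) = 91.8%

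**5. Effect on VE.** If shares a (active) and p (placebo) of cases are later deleted, the expected estimate is about 1 − 0.35×(1−a)/(1−p).
- a = p = 10%: 65.0%, unchanged
- a = 0, p = 10%: 1 − 0.35/0.9 = 61.1%
- a = 10%, p = 0: 1 − 0.35×0.9 = 68.5%

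The one-year model, with the MPD hazard tripled after a case, gives:

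| Hazard tripled in | VE, year rule, 2% per year | VE, year rule, 10% per year |
|---|---|---|
| both arms | 65.0% | 65.0% |
| placebo only | 64.3% | 61.2% |
| active only | 65.7% | 68.4% |

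Censoring at the MPD gives 65.0% in all of these.

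**The case against.** The strongest reply is that this is a small efficiency matter, already partly covered. Four parts of it stand.

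- **The loss is small and assumed.** No MPD rate or timing is in the documents. For MPDs present at vaccination the two rules give the same result, and with a single dose the share arising later is unknown.
- **The sample size already allows for exclusions.** A reader might infer that a 76-event target leaves no slack. The documents do not support that. The 76.3 events are net of 10% exclusions per year, which include protocol violations. The last look is fixed by calendar date (30 April 2023). Local-cohort participants enrolled before the cut-off enter the primary analysis on top of the 23,000 used for sizing.
- **A treatment route from case to deletion is not shown.** A reader might infer that a steroid-treated RSV case would be erased, since "chronic or recurrent use of systemic corticosteroids, or radiotherapy are prohibited throughout the study". Protocol 6.8 says only that the sponsor should be contacted if such use becomes medically indicated, and nothing visible makes it an efficacy-impacting MPD. Corticosteroid prescription during an RSV episode is itself an exploratory endpoint analysed on the PPE (SAP 6.5), which points the other way.
- **MPD dates may be imprecise**, particularly for continuing non-compliance. Immunogenicity samples carry their own dates, so that comparison is not perfect.

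The appeal to the full analysis set (FAS) stands only in part: "As a sensitivity analysis, the above model will be repeated based on the FAS". That analysis keeps the deleted cases, but it also keeps data after the MPD, drops the 14-day onset restriction and starts follow-up at vaccination (SAP 6.3.3). A PPE–FAS difference could not be traced to the year rule. The SAP's analysis of all events rather than first events repeats the first-year-only restriction. No planned analysis isolates the rule.

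**Conclusion.** The point holds as a cheap improvement. The year rule makes the counting of a valid case depend on a later deviation, and it discards follow-up that the deviation cannot have affected. The expected cost is about 0.5% of cases at 1% MPDs per year and about 2.5% at 5%, or under one percentage point of power. This rests on assumed MPD rates, uniform timing and MPDs arising after vaccination; part of the loss may already lie within the planned allowance.

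A reader might infer that the rule biases VE downward, because placebo has more illness and so more deletions. That does not follow, because VE is a ratio. Deleting 10% of cases from each arm of a 31 vaccine / 45 placebo split leaves 27.9 and 40.5, and 1 − 27.9/(2×40.5) = 65.6%, the same as 1 − 31/(2×45). Removing one placebo case alone gives 1 − 31/(2×44) = 64.8%, but that assumes no matching vaccine-arm deletions. Bias needs a chance of an MPD after a case that differs by arm, and it can then go either way. The documents do not show such a difference in this blinded trial.

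**What to change.** In Protocol 9.3 and 9.4.1.1 and SAP Table 3, 6.3.3 and 6.4.1.2.1:

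- For an efficacy-impacting MPD arising after vaccination, count cases with onset before it and censor follow-up the day before it. For a continuing deviation, use its earliest known date.
- Keep full exclusion for MPDs already present at vaccination.
- Keep the present year rule as a sensitivity analysis.

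If the primary analysis has already been run, leave it as it is, add the censored version as a sensitivity analysis, and report by arm the cases removed by the year rule. This remains useful after the termination recorded in SAP 6.11, because LRTD and ARI are still to be analysed per year and over the whole study.

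Reconcile the second-year endpoints: Protocol 9.4.1.2 names first-year MPDs only, while Protocol 9.3 and SAP 6.4.1.2.1 also exclude second-year MPDs. Under censoring, a participant with a second-year MPD would contribute from Day 365 to the day before it.

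The cost is wording in both documents and a date for each MPD, some of which will need a stated convention.

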9.4. Statistical Analyses

The Statistical Analysis Plan will be finalized prior to the first database lock (primary or interim analysis) and it will include a more technical and detailed description of the statistical analyses described in this section. This section is a summary of the planned statistical analyses of the most important endpoints including primary and secondary endpoints.

The analysis plan for the interim and primary analyses is provided in Section 9.5.1.

9.4.1. Efficacy Analysis

9.4.1.1. Primary Endpoint

The analysis of the primary endpoint will evaluate the first occurrence of RT-PCR-confirmed RSV-mediated LRTD (for the definition, see Section 8.2, Efficacy Assessments) with onset of at least 14 days after vaccination in the active vaccine group compared to the placebo group in the PPE population. Time at risk will also be taken into account. The null hypothesis of LL \leq 20% for RT-PCR-confirmed RSV-mediated LRTD will be tested versus the alternative hypothesis of LL $>$ 20%. Additionally, the observed VE should be $>$ 50%.

Exact Poisson regression will be fitted with the event rate, defined as the number of cases (with onset at least 14 days after vaccination) over the follow-up time (off-set) as dependent variable and the vaccination group, being at increased risk of RSV disease, and age stratum (both variables as stratified; see Section 6.3) as independent variables. Each participant will be taken into account in the model with one observation indicating whether they had a case or not, the vaccination group, the stratification factors, and the follow-up time.

The follow-up time is defined as the time between 14 days post-vaccination and occurrence of the first event. For non-cases, it is the time between 14 days post-vaccination and the database cut-off date of the analysis. However, for participants who discontinued or completed the study before that date and before having an event, follow-up time is defined as the time between 14 days post-vaccination and the date of last contact.

For participants with an MPD impacting efficacy during the second year, only the first year data are taken into account: for cases during the first year, the follow-up time is defined as the time between 14 days post-vaccination and occurrence of the first event. For non-cases, it is the time between 14 days post-vaccination and the Day 365 visit. Thus, all participants will be included in the analysis according to their follow-up time.

The study is 92successful if:

- The LL of the 95% 2-sided CI (potentially corrected as described in Section 9.4.1.3) around the VE (1-relative risk rate) calculated from the Exact Poisson regression model is above 20% and additionally a point-estimate of VE >50% is observed for Group 1

Sensitivity Analyses

As a sensitivity analysis, the above model will be repeated based on the FAS, not taking into account the restriction on the onset (at least 14 days). Additional sensitivity analyses will include:

- An exact binomial test, which does not take into account strata or follow-up time, based on the PPE population and the FAS. The VE (1-relative risk) and the corresponding corrected 2-sided CI based on the exact binomial will be calculated as well. The same alpha as in the primary analysis will be used for calculating the CI.
- If the primary analysis is performed in 2023, an exact Poisson model similar to the primary analysis will be performed including an interaction term between the treatment group and the year variables.

The analysis of the primary endpoint will be repeated, but participants with RSV infection and a co-infection with at least one other respiratory virus (ie, confirmed using the BioFire Filmarray Respiratory panel for nasal swabs, or the BioFire Filmarray PN panel for a sputum sample, when available) will not be considered as a case for that episode, as the etiology of symptoms will be indeterminate. Additionally, the analysis of the primary endpoint will be repeated, taking into account only the RT-PCR test results from the study-specified BioFire Filmarray Respiratory panel for nasal swabs and the BioFire Filmarray PN panel for a sputum sample, when available (ie, excluding hospital test results with a locally approved RT-PCR test for participants who were

hospitalized). Details on the strategy for local site and central testing of the nasal swabs and sputum samples are provided in Section 8.2.4. Another sensitivity analysis will focus on the programmed case definition of RT-PCR confirmed RSV-mediated LRTD, not taking into account the CEC adjudication.

